## 8.5 Safety Follow-up

### For patients treated until week 48:

Patients will be instructed to fast prior to the visit. A safety follow-up for all patients will be conducted 4 weeks (+/- 7 days) after the final dose of study medication and will include,

- Physical exam (See Section 8.8.1)
- Blood Pressure and Heart Rate
- Vital signs (See Section 8.8.2)
- ECG (See Section 8.8.3)
- Previous and concomitant treatments
- Adverse Events
- Urinalysis (See Section 8.8.4)
- Blood samples for
  - Serum biochemistry (See Section 8.8.4)
  - Hematology and coagulation (See Section 8.8.4)

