#### **8.7 Assessments and Procedures for Patients who Prematurely Discontinue Study Medication during double-blind treatment period**

Patients who withdraw from study medication should come to the site for a safety follow-up, 4 weeks after the last dose: the same safety assessments as the ones planned for study completer's week 52 visit (V31) should be performed.

Additionally:

- In case the study medication is stopped prematurely prior to week 24 (V18), a 3T-MRI should be performed as soon as possible after study drug discontinuation. If the patient agrees to stay in the study, he/she will be asked to come back at the site for full assessments as per protocol every 8 weeks until visit V30 and a last 3T-MRI will be performed at visit V30.
- In case the study drug is stopped during the extension treatment period (i.e. after week 24 (visit V18), patient should come back to the site for full assessments as per protocol every 8 weeks until week 48, a last 3T-MRI will be done at week 48.

All AEs (related or not related) must be reported until the final study evaluation at visit V30 and thereafter only the SAEs likely to be related to the study drug or study procedures must be notified.

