## **11.4 Adverse Event Reporting**

All observed or volunteered adverse events occurring during the study period, at any time from the signature of the informed consent until the final study evaluation, regardless of treatment group or suspected causal relationship to study drug, will be recorded on the adverse event page(s) of the eCRF.

The need to capture this information is **not dependent** upon whether the adverse event is considered to be related to the use of the study drug. Also, adverse events resulting from concurrent illnesses and reactions to concurrent medications must be reported. In order to avoid vague, ambiguous, or colloquial expressions, the AE will be recorded using standard medical terminology rather than the patient's own words.

Each AE should be described in detail in the eCRF: nature of the event (a sign, a symptom or a diagnosis preferably), onset and stop dates, severity, relationship to study drug, seriousness (see below *Section 11.5*), action taken including corrective therapy and outcome.

AEs that are believed to be at least possibly related to study drug should be followed until satisfactory resolution or acceptable stabilization.

For all AEs, the Investigator must pursue and obtain the necessary information both to determine the outcome of the adverse event and to assess whether it meets one of the criteria for classification as a serious adverse event requiring immediate notification to the **PV Department of ICTA PM** (see *Section 11.5*). For all AEs, sufficient information should be obtained by the Investigator to determine the causality of the adverse event (e.g., study drug or other illness).

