## **11.5 Serious Adverse Events**

### **11.5.1 Definition**

A **Serious Adverse Event (SAE)** is any untoward medical occurrence that at any dose:

1. Results in death;
2. Is life-threatening;
3. Results in patient's hospitalization or prolongation of existing hospitalization;
4. Results in a persistent or significant disability/incapacity; or
5. Results in congenital anomaly/birth defect
6. Is a medically significant event

A **Suspected Unexpected Serious Adverse Reaction (SUSAR)** is a suspected adverse event considered as related to the study drug and which is both unexpected and serious.

Important medical events that may not result in death, be life-threatening, or require hospitalization may be considered as serious adverse events when, based upon appropriate medical judgment, they may jeopardize the patient or may require medical or surgical intervention to prevent one of the outcomes listed above. Examples of such medical events include allergic bronchospasm requiring intensive treatment in an emergency room or at home, blood dyscrasias or convulsions that do not result in patient hospitalization, or the development of drug dependency or drug abuse.

A life-threatening adverse event is any adverse event that places the patient at immediate risk of death from the reaction as it occurred (e.g., it does not include a reaction that, had it occurred in a more severe form, might have caused death).

Initial hospitalization is defined as any inpatient admission (even if less than 24 hours). For chronic or long-term in patients, inpatient admission also includes transfer within the hospital to an acute/intensive care inpatient unit (e.g., from the psychiatric wing to a medical floor, from a medical floor to the coronary care unit, from the neurological floor to the tuberculosis unit).

Inpatient admission in the absence of a precipitating, treatment-emergent, clinical adverse event may meet criteria for “seriousness”, is not considered as an adverse event and thus is not subject to immediate reporting. For example:

1. Admission for treatment of a pre-existing condition not associated with the development of a new adverse event or with a worsening of the pre-existing condition (e.g., for work-up of persistent pre-treatment lab abnormality)
2. Social admission (e.g., patient has no place to sleep)
3. Administrative admission (e.g., for yearly physical exam)

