7.5.1 Adverse events (AE)

AE term (Investigator term) will be assigned to the lowest level term (LLT), and a preferred term (PT) will be classified by a high level term (HLT), a high level group term (HLGT) and a system organ class (SOC) according to the Medical Dictionary for Regulatory Activities (MedDRA) thesaurus, version 19.1 or higher.

An adverse event will be considered as treatment-emergent (TEAE) if AE onset date is between first infusion of CER-001 and last infusion of CER-001 + 28 days, or if AE occurred before the first infusion of CER-001 but gets worse on study treatment. In case of incomplete date(s), see section 7.1.4.

An overview of the number of patients with at least one AE and the corresponding number of AEs will be presented including:

- Any AE
- Any TEAE
- Any serious TEAE
- Any severe TEAE
- Any TEAE leading to dose reduction of the study medication
- Any TEAE leading to temporary discontinuation of the study medication
- Any TEAE leading to permanent discontinuation of the study medication
- Any TEAE related to the study medication (Related = definite, probable or possible)
- Fatal AE
- Fatal TEAE
- Any coronary event (Coronary event = event for which HLGT = Coronary artery disorders)

All PT with HLGT = Coronary artery disorders will be described in the same way in a separate table.

CER-001-CLIN-009 CER-001

Note: recurring AEs (*i.e.* AEs classified with the same Preferred Term (PT)) for a given patient will be only counted once and only their most severe intensity or most severe relationship to the study medication will be described.

TEAEs will also be tabulated by System Organ Class (SOC) and PT. They will be presented according to seriousness (Serious / Not serious), severity (Mild/Moderate/Severe) and relationship with the study medication (Related / Not related). They will finally be tabulated by SOC and PT according to relationship with the study medication within severity.

The different analyses described above will be summarized overall, on the induction period and on the post-induction period (AEs that occurred during maintenance or extension phase). Assignment of AEs to periods will be performed as follows:

Period	Assignment
Induction	Start date of TEAE < date of infusion at W10
	(if day of AE is missing then impute to first of the month)
Post-induction	Start date of TEAE ≥ date of infusion at W10
	(if day of AE is missing then impute to first of the month)

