TEAE leading to death, other SAE (AE leading to death excluded) and other significant AE (any events leading to dose reduction, leading to temporary/permanent discontinuation of the study medication) will also be described on an individual basis. These listings will include the following information:

- Randomization group
- Patient identifier
- Age, race, ethnicity, sex, weight at inclusion
- Investigator's reported term, preferred term
- Duration of the adverse event
- Severity
- Seriousness
- Action taken
- Outcome
- Relationship with the study medication
- Timing of onset of the adverse event in relation to last dose of study medication
- Study treatment at time of event or most recent study treatment taken
- Study drug dose in absolute amount
- Total number of infusions received

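### The SAP's individual safety listings leave out a fatal adverse event that is not treatment-emergent, although a non-fatal SAE with the same onset would be listed

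*SAP*

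**What the plan says.** SAP 7.5.1 sets out three categories of event for individual description: "TEAE leading to death, other SAE (AE leading to death excluded) and other significant AE". The third is defined by its effect on dosing, namely events causing a dose reduction or "leading to temporary/permanent discontinuation of the study medication) will also be described on an individual basis". The fields for these listings include timing of onset relative to the last dose, treatment at the event, absolute dose and total number of infusions.

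The same section calls an event treatment-emergent "if AE onset date is between first infusion of CER-001 and last infusion of CER-001 + 28 days", or if it was present before the first infusion and worsened on treatment. Its overview table has separate rows for fatal AEs and fatal TEAEs.

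On follow-up, Protocol 8.5 says "A safety follow-up for all patients will be conducted 4 weeks (+/- 7 days) after the final dose of study medication". For patients who stop study drug after week 24, Protocol 8.7 says "patient should come back to the site for full assessments as per protocol every 8 weeks until week 48". For those who stop before week 24, the return visits depend on the patient agreeing to stay. Protocol 8.7 has all AEs reported until V30, which is W48 in Appendix A.

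**The concern.** The first listing takes in events by the term TEAE, and the second excludes them by the wider term AE. The two sets are not complementary, and a fatal AE that is not treatment-emergent lies between them. The result is inverted: a late non-fatal SAE receives the full case description and a late fatal one does not.

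Safety over 24 weeks is one of the two primary objectives, and with 30 patients a single death is a principal safety result. For a death after early stopping, the interval since the last dose and the amount of drug received are what a reader needs to judge relatedness. The dedicated listing is where the SAP undertakes to show them together.

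**Working it through.** The plan gives no figure to reproduce. The check is set logic on the definitions, followed by date arithmetic for the time in which the case can arise.

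**Logic.** Let F be fatal AEs, T treatment-emergent AEs and S serious AEs.

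- Protocol 11.5.1 makes an event serious if it "Results in death", so F lies inside S.
- Listing 1 = F and T.
- Listing 2 = S and not F.
- Listings 1 and 2 together therefore cover all of S except F and not T.
- The SAP treats F and F-and-T as different sets, because its overview counts them on separate rows.
- Listing 3 does not reliably catch the remainder. An event starting more than 28 days after the last infusion would not normally cause a dose change in a drug already stopped.
- If listing 1 covered all of F, listings 1 and 2 together would equal S and the remainder would be empty.

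**Can the case occur?** AEs are collected "at any time from the signature of the informed consent until the final study evaluation" (Protocol 11.4). Deaths before dosing are outside the safety population (SAP 6.1), so the practical case is late onset in a dosed patient.

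- Last infusion at W0: the window closes at W4 and AEs are collected to W48, leaving 48 − 4 = 44 weeks.
- Last infusion at W22: the window closes at W26, leaving 48 − 26 = 22 weeks.
- Completer with a safety visit at day 28 + 7 = 35: onsets on days 29 to 35 are outside the window, at most 7 days per patient.

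The protocol's own TEAE definition (11.1) has no upper time limit, so the case arises from the SAP's 28-day window. The SAP states that it supersedes the protocol. Its section 10, which records modifications, mentions only the efficacy model.

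**Size among early stoppers.** Protocol 12.4 plans for 20% discontinuation: 0.20 × 30 = 6 patients, of whom 4 are on CER-001 at 2:1. Assume that all six are drug-stoppers and that the week w of the last infusion is uniform on 0 to 48. The gap per stopper is max(0, 48 − (w + 4)) = max(0, 44 − w).

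| Follow-up assumption | Mean gap per stopper (weeks) | Six stoppers (patient-weeks) | Four on CER-001 (patient-weeks) |
|---|---|---|---|
| All stay to W48 | 44² / (2 × 48) = 20.2 | about 121 | about 81 |
| None stopping before W24 stays | 20² / (2 × 48) = 4.2 | about 25 | about 17 |
| All six leave the study | near 0 | near 0 | near 0 |

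In the second row only stops from W24 to W44 contribute, hence 44 − 24 = 20 in the numerator.

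**The case against.** The strongest reply is that the death remains visible. It is counted in the overview row for fatal AEs. Protocol 12.3.2 lists every AE with course, severity, relationship and outcome, and SAP 7.7 lists all collected data used in the analysis. Every death is also an SAE reported within 24 hours on its own form. The infusion dates, doses and volumes feed the exposure calculations in SAP 7.3, so a reader could assemble the case from the general listings. This stands. A reader might infer from 7.5.1 that such a death would be missed, and the documents do not support that. What they do not promise is the specified fields shown together for that patient.

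Second, the gap is narrow. It turns on the onset of the event and not on the date of death, so a fatal event starting within 28 days of the last infusion is listed however late the patient dies. This also stands.

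Third, 121 patient-weeks should not be read as the expected exposure. Protocol 12.4 uses the 20% as the loss from 30 randomized to 24 completers, and Protocol 9.12 defines a discontinuation as ceasing participation in the study. The plan does not say that these six are drug-stoppers who remain in follow-up. Only the range is supportable, and patient-weeks are not deaths, since no fatality rate is given.

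Two other readings go too far or do not help. Because the window is tied to infusions of CER-001, a reader might infer that no placebo event is ever treatment-emergent in the double-blind phase. SAP 7.1.4 classifies events against study drug dates, and the AE table template in 12.1 has a placebo column, so this is better taken as loose drafting. Nor does it close the gap to suppose that TEAE governs all three categories. The text drops the term after the first, and that reading would leave out late non-fatal SAEs as well.

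**Conclusion.** The point holds as a minor reporting correction. On the text of SAP 7.5.1, a fatal AE in a dosed patient with onset more than 28 days after the last infusion, and not a pre-existing event that worsened on treatment, is in neither of the first two individual listings. This follows from the wording and needs no assumption.

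The amount of exposed time does rest on assumptions. Among early stoppers it runs from near 0 to about 121 patient-weeks, with about 25 if only those stopping after W24 are followed. This depends on whether the 20% are drug-stoppers who stay in follow-up, on stop times being uniform over 48 weeks, and on patient agreement before W24. In completers it is at most seven days each. The number of deaths affected cannot be estimated from the documents and may well be none. No efficacy result and no summary count changes.

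**What to change.** In SAP 7.5.1, widen the first category to AEs leading to death, for all onset dates in the safety population, with a column flagging each as treatment-emergent or not. Keep the exclusion of fatal AEs from the other-SAE listing. The two listings then cover every SAE in dosed patients exactly once.

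While the section is open, wording the treatment-emergent window in terms of study drug would remove the ambiguity for placebo patients.

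The cost is one wording change and one flag column. No new data are needed, and it can be done before database lock with the planned dry-runs of the outputs.

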7.5.2 Vital signs, physical examination, ECG

Clinical examination and vital signs will be summarized at each time point (screening, W0 (baseline), W4, W8, W16, W24, W32, W40, W48, 4 weeks after last dose). In addition, absolute changes from W0 (baseline) will be calculated at each post-baseline time point. Absolute change at Wi is defined as follows: Value at Wi - Value at W0.

- Respiratory rate (breaths/min)
- Systolic blood pressure (mmHg)
- Diastolic blood pressure (mmHg)
- Heart rate (beats/min)
- Body temperature (°C)
- Body weight (kg)
- Body mass index (kg/m²)

ECG diagnosis (Normal / Abnormal, not clinically significant (NCS) / Abnormal and clinically significant (CS)) will be summarized at screening and presented through shift tables from W0 (baseline) for the following time points: W4, W8, W16, W24, W32, W40, W48, 4 weeks after last dose).

In case of abnormal result regarding ECG (clinically significant or not) for a given patient, a listing will be produced including patient's identification, visit, date of assessment, ECG diagnosis, specification for the result and remarks, whatever the visit.

Assessment of physical examination (Normal / Abnormal non-clinically significant / Abnormal clinically significant) will be described at screening and presented through shift tables from W0 (baseline) for the following time points: W4, W8, W16, W24, W32, W40, W48, 4 weeks after last dose).

In case of missing value at W0 for a variable, imputation will be performed using the value obtained at screening. This imputation will be performed for shift tables only and absolute changes.

Shift tables will be:

- No change (from normal to normal / from abnormal NCS to abnormal NCS / from abnormal CS to abnormal CS)
- Improvement (from abnormal NCS to normal / from abnormal CS to abnormal NCS / from abnormal CS to normal)
- Deterioration (from normal to abnormal CS / from normal to abnormal NCS / from abnormal NCS to abnormal CS)

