## **SAFETY AND TOLERANCE**

- Incidence and severity of AEs from routine monitoring
- Incidence of abnormalities and changes from baseline in clinical laboratory parameters from testing of blood and urine
- Incidence of adverse changes from baseline vital sign values
- Incidence of adverse changes from baseline physical examinations
- Safety parameters will also be summarized by genetic subset to identify possible trends

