### **12.3.1 Safety and Tolerance Variables**

Safety and tolerance variables will include:

- Incidence, severity and causality of AEs and particularly coronary events
- Change from baseline in physical examinations, clinical laboratory tests, vital signs and ECGs

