### **12.3.2 Analysis of Safety and Tolerance Variables**

Descriptive statistics will be provided for all safety parameters.

Adverse events will be coded by body system and preferred term based on the Med-DRA dictionary of standardized terminology. All AEs reported during the study will be listed, documenting course, severity, relationship to study drug and outcome. Adverse events will be tabulated by study treatment.

Summary tables will give the number and proportion of patients who experienced an AE, broken down by body system, preferred term and maximum severity. Related adverse events, defined as those adverse events that are possibly, probably or definitely related to study drug, will be summarized similarly.

Laboratory parameters, vital signs, physical exam results, and ECG findings will be summarized by treatment group and time point using descriptive statistics (n, mean, standard deviation, median and range), or frequencies and percentages, as appropriate. Results will be classified as normal or abnormal at screening and at on-treatment and follow-up visits. Shift tables of these values will be provided to summarize the change between screening and on-treatment / follow-up for each treatment group.

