7.7 Listings of individual data

All collected data and derived variables used for the statistical analysis will also be presented in individual patient listings, in accordance with ICH appendix 16.2. Each patient will be identified in these listings by his/her unique patient number.

8. Interim analyses

No interim analysis is planned.

9. Data and Safety Monitoring Board

The Data and Safety Monitoring Board (DSMB) will formally review unblinded study safety data to ensure there is no avoidable increased risk for harm to patients. Analyses for the DSMB meetings will be performed by an independent statistician (different from the one who will perform the final analysis). A specific SAP displays the safety data generated needed for the DSMB review.

10. Modifications with respect to the protocol

Analysis of efficacy endpoints

Statistical analysis of the primary and secondary outcomes (changes from baseline) were modified with respect to the protocol. In order to gain in terms of power, model will be fitted using all observations available for each patient during the study. Hence, linear mixed model with repeated measures will be used instead of analysis of covariance, Changes from baseline for a specified outcome could therefore be estimated at different time points based on the same model.

CER-001-CLIN-009 CER-001

11. Approval of the Statistical Analysis Plan

ICTA PM	SPONSOR
Project Manager:	Sr VP Clinical Development & Operations:
[name]	[name]
Date:	Date:
Signature:	Signature:
Biostatistician:	
[name]	
Date:	
Signature:	
Head of Medical and Scientific Development:	
[name]	
Date:	
Signature:	

CER-001-CLIN-009

12. Appendices

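### SAP 7.5.2 omits, without declaring it, the normal/abnormal classification and shift tables that protocol 12.3.2 requires for vital signs

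*SAP*

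**What the plan says.** **Protocol.** The synopsis, under Safety and Tolerance, lists "Incidence of adverse changes from baseline vital sign values". Section 12.3.1 describes the variable differently: "Change from baseline in physical examinations, clinical laboratory tests, vital signs and ECGs". Section 12.3.2 then sets the analysis for four domains together: "Laboratory parameters, vital signs, physical exam results, and ECG findings will be summarized by treatment group and time point using descriptive statistics". It continues: "Results will be classified as normal or abnormal at screening and at on-treatment and follow-up visits", and "Shift tables of these values will be provided to summarize the change between screening and on-treatment / follow-up for each treatment group".

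**SAP.** Section 7.5.2 opens with "Clinical examination and vital signs will be summarized at each time point" and adds "In addition, absolute changes from W0 (baseline) will be calculated at each post-baseline time point". The list that follows covers respiratory rate, systolic and diastolic blood pressure, heart rate, temperature, weight and body mass index. Shift tables are then specified for ECG diagnosis and for physical examination. Section 7.5.3 specifies them for laboratory parameters.

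The SAP introduction states that the SAP supersedes the protocol and that changes will be reported in section 10. The only change reported there concerns the efficacy model: "Statistical analysis of the primary and secondary outcomes (changes from baseline) were modified with respect to the protocol".

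**The concern.** Safety and tolerability over 24 weeks is one of the two primary objectives (protocol 4.1, SAP 1.1). Protocol 11.6 names falls and rises in blood pressure and a fall in body temperature among the symptoms of anticipated allergic-type reactions. Protocol section 5 says that infusion reactions occurred more often with CER-001. Such changes affect single patients at single visits. Classification and shift tables show how many patients in each arm moved from normal to abnormal, whereas per-visit averages do not.

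Because the SAP takes precedence, the protocol's table for this domain would not be produced, and no document would record that it had been dropped. If limits for an abnormal value were chosen after unblinding, the count would be post hoc.

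**Working it through.** No stated figure in the plan is at issue, so the check is mainly a comparison of texts.

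**Step 1: the four domains side by side.**

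| Domain | Protocol 12.3.2 | SAP |
|---|---|---|
| Laboratory | Classify; shift table by arm | 7.5.3: shift tables and absolute changes |
| ECG | Classify; shift table by arm | 7.5.2: three-level diagnosis, shifts from W0, listing of abnormal results |
| Physical examination | Classify; shift table by arm | 7.5.2: three-level assessment, shifts from W0 |
| Vital signs | Classify; shift table by arm | 7.5.2: descriptive statistics and absolute change from W0 |

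Vital signs are the only domain without a classification or shift table. Template Table 10 in the SAP appendix is a generic shift layout and does not name them. SAP 7.1.4 mentions shifts from baseline under a heading that includes vital signs. However, it only gives a rule for a missing W0 value, and no vital-sign category is defined anywhere.

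**Step 2: what remains visible.** SAP 7.1.2 gives mean, SD, quartiles, median, minimum and maximum. SAP 7.7 adds individual listings. An extreme value can therefore be found. What is missing is the number of patients affected, by arm and across visits.

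**Step 3: illustration of dilution.** The inputs are 30 patients randomized 2:1 (protocol 6.4), so about 20 and 10. The single-patient fall in systolic pressure is an assumption, varied from 20 to 40 mmHg. The shift in an arm mean is fall / n.

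- CER-001: 20/20 = 1.0, 30/20 = 1.5, 40/20 = 2.0 mmHg.
- Placebo: 20/10 = 2.0, 30/10 = 3.0, 40/10 = 4.0 mmHg.

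For scale, assume an SD of change of 10 to 15 mmHg. The standard error of the arm difference is SD × √(1/20 + 1/10), which is 3.87 to 5.81 mmHg. A shift of 1.5 mmHg is then 1.5/5.81 = 0.26 to 1.5/3.87 = 0.39 standard errors.

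**Step 4: can the missing table be programmed as the documents stand?** Three inputs are unsettled.

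- Limits: neither document defines a normal or abnormal vital sign for analysis.
- Reference: protocol 12.3.2 takes shifts from screening, while the SAP uses W0.
- Reading: protocol 8.8.2 and Appendix A have blood pressure and heart rate taken before and after infusion at weeks 4, 8, 16, 24, 32, 40 and 48. SAP 7.5.2 defines change as a single visit value minus W0 and does not say which reading is used. This ambiguity affects the planned absolute changes too.

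**The case against.** The strongest reply is that the protocol is not uniform and that the SAP meets part of it. The incidence wording is one synopsis bullet. Section 12.3.1 asks only for change from baseline, which SAP 7.5.2 delivers. The synopsis paragraph on safety evaluation asks for summary statistics or frequencies as appropriate. A reader might infer that the protocol fixes incidence as the vital-sign endpoint and that the SAP abandons it; the documents do not support that. What stands is narrower: 12.3.2 names vital signs and requires classification and shift tables for them.

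A reader might also infer that isolated abnormalities would go unseen or entirely uncounted. That is too strong as well. A 30 mmHg fall would give a minimum change of −30 or lower for that arm and visit. Protocol 11.1 has clinically significant abnormal objective findings recorded as adverse events, and SAP 7.5.1 tabulates patients with treatment-emergent events. The gap is confined to readings not reported as adverse events, which depends on investigator judgement.

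Two further points are fair. The paired readings cover 7 of the 29 infusions, whereas adverse events are checked at every infusion visit, so a vital-sign count is not the main detector of infusion reactions. And a count would not be decisive: 2/20 versus 0/10 has a two-sided Fisher p of (190 + 45)/435 = 0.54. Safety analysis here is descriptive, however, and the count is wanted for description.

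**Conclusion.** The inconsistency is real, undeclared and minor. Protocol 12.3.2 requires a normal/abnormal classification and shift tables by arm for vital signs, SAP 7.5.2 does not provide them, and SAP section 10 is silent. Abnormalities not reported as adverse events would be visible in extremes and listings but not counted by patient and arm.

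This conclusion rests on the text alone. The dilution figures are illustrative and depend on the assumed falls and SD. The primary efficacy result does not change. Part of the gap lies in the protocol, which gives no limits for an abnormal vital sign and describes the variable in more than one way.

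**What to change.** In SAP 7.5.2, before unblinding:

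- Add for each vital sign a normal/abnormal classification, a shift table by treatment group, and the number and percentage of patients in each arm with at least one on-treatment abnormal value.
- Have the sponsor set the category limits while blinded. The blood-pressure and heart-rate values in the exclusion criteria were written for eligibility and should not be adopted by default.
- State the reference visit, screening or W0.
- State whether the pre- or post-infusion blood-pressure and heart-rate reading is analysed, preferably tabulating both.
- Reconcile the synopsis bullet, protocol 12.3.1, protocol 12.3.2 and SAP 7.5.2. If the sponsor prefers to keep descriptive statistics only, declare and justify this in SAP section 10.

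The cost is one or two extra tables from data already collected, some SAP wording, and agreement on limits before the blind is broken.
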